2. STUDY OBJECTIVES AND ENDPOINTS

Primary Objective:

1. Evaluate the effects of Crisaborole on itch and night-time scratch (as measured by accelerometry/actigraphy and Observer Reported Itch Assessment (3 months - \leq 11 years old) in children with mild to moderate AD between the ages of 3 months to \leq 11 years old.

Secondary Objectives:

1. Evaluate the effects of Crisaborole on sleep in children ages 3 months to \leq 11 years with mild to moderate AD.
2. Evaluate sleep in primary caregivers.
3. Evaluate the QoL measures in response to Crisaborole treatment (children 3 months to \leq 11 years).
4. Evaluate QoL measures in response to the child's treatment, to the parents/caregivers/families.
5. Evaluate the effect of crisaborole treatment on AD signs, symptoms and severity in children ages 3 months to \leq 11 years with mild to moderate AD.

Exploratory Objectives:

1. Evaluate changes in skin biomarkers in response to Crisaborole treatment in children ages 3 months to \leq 11 years with mild to moderate AD.
2. Evaluate changes in Digital Health Technologies -assessed movement and agitation in children (aged 3 months to \leq 11 years) in response to crisaborole treatment.
3. Evaluate the participant burden and compliance of use of the devices.
4. Evaluate the agreement between ORIA and Patient Reported Itch Severity Scale in children between the ages of 6 to \leq 11 years old

ENDPOINTS

Endpoints:

Final experimental report and a copy of all data, including these endpoints:

Primary Endpoint:

- Daily night-time scratch (Number of scratching episodes, Duration of scratching) as measured by the accelerometry/actigraphy (optional for children participants who have active AD on location of device placement, with a minimum of at least one wrist device needed for enrollment) and the Observer Reported Itch Assessment (ORIA; 3 months - \leq 11 years old) for the AD infant and child population.

Secondary Endpoints:

- Sleep:
 - Nighttime Sleep Quantity (as measured by accelerometry/actigraphy; Children ages 3 months to \leq 11 years and Caregivers ages 18-75 years; devices will be optional for children participants who have active AD on location of device placement, with a minimum of at least one wrist device needed for enrollment)
 - Total Sleep Opportunity
 - Total sleep time
 - Percent time asleep
 - Wake after sleep onset (WASO)
 - Sleep onset latency
 - Arousals from sleep

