- Modified Medical Outcomes Study Sleep Scale (MOS-Sleep; Caregivers- ages 18-75)
 - Children's Sleep Health Questionnaire (CSHQ); ages ≥ 4 - ≤ 11 years) OR Brief Infant Sleep Questionnaire (BISQ; ages 3 months- <4 years)
- PRO/ ObsRO
 - Disease Severity:
 - Observer Global Impression of Severity (OGIS)
 - Observer Global Impression of Change (OGIC)
 - Observer-reported Patient Oriented Eczema Measure (POEM)
- HRQoL
 - Dermatitis Family Impact Questionnaire (DFI; Caregivers of participants ages 3 months - ≤ 11 years)
 - Children's Dermatology Life Quality Index (CDLQI; participants ages ≥ 4 - ≤ 11 years) OR Infants Dermatitis Quality Of Life Index (IDQOL; caregivers of participants ages 3 months- <4 years)

Exploratory Endpoints:

- Device Comfort
 - Device Comfort Questionnaire (Caregivers ages 18-75)
 - Observer Device Comfort Questionnaire (ages 3 months - ≤ 11 years)
- Mobile Device Proficiency Questionnaire (MDPQ; Caregivers ages 18-75)
- Faces, Legs, Activity, Cry, and Consolability Scale (FLACC) (ages 3 months - 5 years)
- Peak Pruritis NRS (Caregivers)
- Patient Reported Itch Severity Scale (6 years - ≤ 11 years old)
- Skin biomarkers (as measured by Tape Stripping)
- Digital Health Technologies -assessed movement and agitation in children as measured by Actigraphy/accelerometry (ages 3 months- ≤ 11 years)
 - Movement (Accelerometry/actigraphy)
 - Temperature

DEVICE ENDPOINTS

GENEActiv Wrist Accelerometry Device (50 Hz sampling rate)

- Accelerometry Raw Data in x, y, and z
- Units of g and collected at 50Hz
- Ambient light level (lux)
- Out of Bed time (hh:mm)
- Wake duration (mins)
- Non wear time (mins)
- Sedentary activity time (mins)
- Light activity time (mins)
- Moderate activity time (mins)
- Vigorous activity time (mins)
- Sedentary activity (%)
- Light activity (%)
- Moderate activity (%)
- Vigorous activity (%)
- Sedentary activity estimated MET.mins

- Light activity estimated MET.mins
- Moderate activity estimated MET.mins
- Vigorous activity estimated MET.mins
- Number of Vigorous periods (> 10 mins)
- Going to bed time (hh:mm)
- Bed duration (mins)
- Total sleep time (mins)
- Sleep efficiency (% total sleep time divided by total time in bed)
- Number of Active periods
- Median activity period (mins)
- Temperature
- Actigraphy Digital Health Technology (ages 3 months - ≤ 11 years)
 - Actigraphy at 25 Hz (X,Y,Z movement)

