Approximately 270 children, age 3 months to ≤ 11 years, and their primary caregiver as participants, for a total of 540 participants (270 pairs), will be randomized in 1:1 ratio to either Crisaborole (2% BID) or vehicle treatment and will be followed for 2 weeks, with an objective of approximately 50% of recruited child participants being ages 5 years old or younger. For this study, we will employ a simple randomization procedure. Participants will be randomly assigned (1:1) using computerized random numbers to receive either crisaborole or the vehicle. The participants will be asked to apply a thin even-layer of Crisaborole 2% or vehicle twice daily (excluding mouth, eyes, and vagina, per label), to all locations with active lesions and record location and time of application on the daily dosing form (as identified on the Dosing Record Sheet, breastfeeding women will be instructed to use the provided gloves when applying crisabrole/vehicle). The study will be comprised of an initial screening/baseline visit for children participants who have an existing diagnosis of symptomatic AD, screened and enrolled in the study along with their primary caregivers after signing an informed consent (or parents/guardians and assent when appropriate). Upon enrollment child participants and caregiver participants will complete a one week acclimation and training phase, where the children will not be on medication, for wearing accelerometry/actigraphy and performing observer-reported outcome assessments (caregivers for participants) and self-reported outcome assessments (caregivers). After the one week acclimation and training phase, the child participants will be on a Crisaborole or vehicle treatment for two consecutive weeks. During those 2 weeks, the children, 3 months up to <2 years will wear one actigraphy or one accelerometry device on each wrist and one actigraphy or one accelerometry device on each ankle (optional for those who have active AD on location of device placement, with a minimum of at least one wrist device needed for enrollment). Children 2 years to ≤ 11 years will wear one actigraphy or one accelerometry device on each wrist (optional for those who have active AD on location of device placement, with a minimum of at least one wrist device needed for enrollment). The primary caregiver (parents/guardians) will also wear one accelerometer device on each wrist and complete daily assessments related to scratching, sleeping habits, pain, AD severity, quality of life, and device comfort questionnaires (parent/guardian will complete as appropriate). The participants will be asked to return to the laboratory

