- Investigator's Static Global Assessment (ISGA) (scored by a dermatologist or a medically qualified individual who has been trained in the assessment; rater to be consistent throughout study)
- EASI assessment (scored by a dermatologist or a medically qualified individual who has been trained in the assessment; rater to be consistent throughout study)
- Calculate % body surface area (BSA) affected with AD
- Childhood Asthma Control Test
- Tape Stripping (Biomarker Assessment)
- Observer Reported Itch Assessment (ORIA; ages 3 months - ≤ 11 years)
- Patient Reported Itch Severity Scale (ages 6 years to ≤ 11 years old)
- Observer Global Impression of Severity (OGIS; ages 3 months - ≤ 11 years)
- Peak Pruritis NRS (Caregivers)
- Children's Sleep Health Questionnaire (CSHQ; ages ≥4-≤ 11) OR Brief Infant Sleep Questionnaire(BISQ; ages 3 months-<4 years)
- Medical Outcome Sleep Scale (MOS; caregivers only)
- Mobile Device Proficiency Questionnaire (MDPQ; caregivers only)
- Faces, Legs, Activity, Cry, and Consolability Scale (FLACCS)
- Dermatitis Family Impact Questionnaire (DFI; parent/guardian(s); ages 3 months- ≤ 11 years)
- Children's Dermatology Life Quality Index (CDLQI; ages ≥4-≤ 11 years) OR Infants Dermatitis Quality Of Life Index (IDQOL; ages 3 months-<4 years)
- Observer-reported Patient-Oriented Eczema Measure (POEM); ages 3 months – ≤ 11 years)
- The participant will be asked to don the accelerometry/actigraphy devices (coordinator will log dispensing) as follows: The participant will be provided the accelerometry/actigraphy devices immediately after completion of informed consent and will be trained. Devices will be optional for child participants who have active AD on location of device placement, with a minimum of at least one wrist device needed for enrollment.
 - Accelerometry
 - Children: Ages 2 years to ≤ 11 years; On R & L wrists
 - Caregivers: Ages 18 to 75 years; On R & L wrists
 - Actigraphy or accelerometry:
 - (Ages 3 months up to ≤ 11 years; On R & L wrists and R & L ankles for 3 months - <2 years; R & L wrists only for 2 – ≤ 11 years)

Out-of-Laboratory (At-Home) Assessments (Days -7–Day 1; Between Visits 1 & 2):

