8.2 Safety Review

Safety review for this study will be accomplished throughout the study and monitor all study activities identified in the schedule of activities. Risks to be monitored include: hypersensitivity, application site pain, application site discomfort, skin irritation, pyrexia, upper respiratory tract infection, diarrhea, cough, and any unknown risks or unanticipated problem identified in the performance of the study. This will be accomplished by study staff personnel as part of each visit activity, spontaneously reported by the caregivers, and monitored for all participants enrolled throughout the study. Specifically during each study visit, study staff will assess the level of skin irritation and participant reported discomfort (or AD flare up) from both the wearing of devices and/or subsequent topical application of crisaborole/vehicle. The Principal Investigator will be notified of any AEs immediately. All other reporting plans are outlined in section 8.3.

Signs of AD (based on % BSA) will be measured and evaluated throughout the study period on laboratory visits 3, 4, and 5 (days 2, 8, 15) by the study dermatologist. Participants whose BSA exceeds 40% at visits 3 and 4, will be instructed to terminate the use of vehicle/crisaborole and will be withdrawn from the study. We will monitor collected BSA percentages at each time point and their change from baseline. Participants will also be provided with a 24/7 phone number should they need to contact the laboratory after hours.

Appropriate documentation of any and all identified unanticipated or adverse events will be properly reported to the IRB including appropriate mitigation and reports for recommended changes, with unanticipated problems within 7 days. A document listing any identified safety related events will be maintained and monitoring of this list will be ongoing throughout the study as a means to track and review these events (accomplished by comparative analysis of each event in comparison to all other events throughout the study) to determine expectedness, relatedness, or suggestion of new risks that may have been identified. Other events will be documented, assessed and monitored by staff and investigators and reported at the time of continuing review. Monthly reviews of blinded adverse events will be

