How often during the past week did you...

Get the amount of sleep you needed?

All of the time
Most of the time
Some of the time
A little of the time
None of the time

Subject ID: _____

Date: _____

Technician Initials: _____

Device Comfort Questionnaire

- Please rate the overall comfort of the wrist device sensors where 0 means that they were only tolerable enough to participate in the study and 5 means that you did not notice them once the study began. (Circle one)

0 1 2 3 4 5

- Were the sensors' locations that were used (e.g., wrist) particularly comfortable? (Circle one)

Yes No

- How likely are you to be willing to wear the wrist device continuously, at home, for multiple days? (Circle one) Very unlikely Unlikely Likely Very Likely

Observer Device Comfort Questionnaire

- Please rate the overall comfort of the wrist device sensors for your child, where 0 means that they were only tolerable enough to participate in the study and 5 means that they did not notice them once the study began. (Circle one)

0 1 2 3 4 5

- Were the sensors' locations that were used (e.g., wrist) particularly comfortable for your child? (Circle one)

Yes No

- How likely is your child to be willing to wear the wrist device continuously, at home, for multiple days? (Circle one)

Very unlikely Unlikely Likely Very Likely

Subject ID: _____

Date: _____

Technician Initials: _____

PAD Brief Infant Sleep Questionnaire (BISQ)

Please mark only one (most appropriate) choice, when you respond to items with a few options.

Name of Responder: **KEEP BLANK** Date: _____

Role of Responder: Father Mother Grandparent Other, Specify: _____
Name of the child: **KEEP BLANK** Date of Birth: Month 1 Day: 1 Year: _____

Sex: Male Female Birth order of the child: Oldest Middle Youngest

Sleeping arrangement:

Infant crib in a separate room Infant crib in parents' room
 In parents' bed Infant crib in room with sibling
 Other, Specify: _____

In what position does your child sleep most of the time?

On his/her belly On his/her side On his/her back

How much time does your child spend in sleep during the NIGHT (between 7 in the evening and 7 in the morning)? Hours: _____ Minutes: _____

How much time does your child spend in sleep during the DAY (between 7 in the morning and 7 in the evening)? Hours: _____ Minutes: _____

Average number of night wakings per night:

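### The Observer Device Comfort Questionnaire has no graded rating of the ankle devices worn by children under 2

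*Combined protocol and SAP*

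**What the plan says.** Under Sections 3 and 5, children aged 3 months to under 2 years have both wrists fitted, plus "one actigraphy or one accelerometry device on each ankle (optional for those who have active AD on location of device placement", subject to at least one wrist device for enrolment. The Visit 1 procedures in Section 5 repeat the placement: "On R & L wrists and R & L ankles for 3 months - <2 years". Children from 2 to 11 years, and caregivers, wear devices on the wrists only.

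Exploratory objective 3 in Section 2 is to "Evaluate the participant burden and compliance of use of the devices". The matching device comfort endpoint for the children is the "Observer Device Comfort Questionnaire (ages 3 months - ≤ 11 years"), which the Schedule of Activities places at V05 only.

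The form, in the appendix of PRO/ObsRO assessments, has three items:

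- Item 1, scored 0 to 5: "Please rate the overall comfort of the wrist device sensors for your child".
- Item 2, a single yes or no, on whether the sensors' "locations that were used (e.g., wrist) particularly comfortable for your child".
- Item 3, four levels from very unlikely to very likely: "How likely is your child to be willing to wear the wrist device continuously, at home, for multiple days".

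**The concern.** The instrument does not match the devices worn in the one age group that has ankle devices. The two items that carry a scale both name the wrist, and the word ankle appears nowhere on the form. The items parallel those of the caregiver form, where wrist-only wording is right because caregivers wear nothing on the ankles. It does not carry over to infants and toddlers.

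What is at stake is the burden half of exploratory objective 3. If the plan is followed exactly, the study will report comfort and willingness for under-2s as though they wore wrist devices alone. A negative answer to item 2 cannot be assigned to wrist or ankle. It also gives no degree of discomfort, since the question is whether the locations were especially comfortable. Section 8.4 itself names ankle devices as a possible source of physical discomfort, so the missing rating concerns a burden that the protocol already expects.

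**Working it through.** This is mainly a comparison of texts. The plan states no figure to reproduce.

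**Step 1. What each ODCQ item can say about each site.**

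| Item | Response | Wrist | Ankle |
|---|---|---|---|
| 1, comfort | 0 to 5 (6 levels) | graded | none |
| 2, locations used | yes/no | pooled | pooled |
| 3, willingness | 4 levels | graded | none |

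Graded items: 2 of 3. Graded items on the wrist: 2. Graded items on the ankle: 0.

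**Step 2. Whether another record supplies the missing score.** Section 8.2 says that at each visit "study staff will assess the level of skin irritation and participant reported discomfort (or AD flare up) from both the wearing of devices". That is a safety check, and it sets out no score by body site. Adverse events are graded in the same section, but the grades are too coarse to stand in for a comfort scale: mild means that no discomfort was reported, and severe requires discomfort leading to withdrawal. Section 8.4 lets a child continue without an uncomfortable device, which records an outcome and not a rating. None of these asks about willingness to wear an ankle device. No other form in the appendices does so.

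**Step 3. Share of a child's devices with no graded rating.** With *w* wrist devices (1 or 2; at least one is required) and *a* ankle devices (0, 1 or 2), the share is a / (w + a):

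| | a = 0 | a = 1 | a = 2 |
|---|---|---|---|
| w = 2 | 0/2 = 0% | 1/3 = 33% | 2/4 = 50% |
| w = 1 | 0/1 = 0% | 1/2 = 50% | 2/3 = 67% |

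The full set gives 50%, and the range is 0% to 67%.

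**Step 4. How many children are affected.** Section 3 aims for about half of the 270 children to be 5 or younger: 0.50 × 270 = 135. Under-2s are some part of that group. The documents give neither the number under 2 nor the number expected to wear an ankle device, so 135 does not size the affected group.

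**Step 5. What else could be touched.** Section 9 analyses the scratch endpoints from the devices in ages 2 to 11, who wear wrist devices only. The sample size rests on the itch score. The specific analyses listed at the end of Section 9 do not mention device comfort.

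**The case against.** The strongest reply is that no commitment is broken. Objective 3 does not promise graded scores or scores by body site, and the endpoint is simply the questionnaire as it stands. Item 2 asks about all locations used and offers the wrist only as an example, so the ankles are covered after a fashion. No listed analysis needs an ankle score. Real intolerance of an ankle device would surface through the visit checks, the adverse event records or removal of the device. On this view the request is a preference for finer detail on an exploratory form.

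Much of this stands, and it sets the weight of the point. The gap is descriptive and exploratory, and no decision in the plan turns on it. The percentages in the working are shares of devices on one child and do not measure lost precision. The 67% case needs a combination of devices whose frequency is unknown.

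What does not stand is the claim that the gap is already filled. A pooled yes/no cannot separate ankle from wrist, and safety records detect harm without measuring comfort. The objective refers to the devices without limiting them to the wrist, and the form as written cannot produce the ankle half of the answer.

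A further objection is that a caregiver can only guess at an infant's willingness to wear an ankle device. That is fair, but the form already asks for the same guess about the wrist. Asking it for both sites at least makes the two comparable.

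**Conclusion.** The concern holds. Neither of the two graded ODCQ items addresses the ankle. For an under-2 wearing the full set, half of the devices (2 of 4) therefore have no graded rating, and the burden part of exploratory objective 3 is only partly answered for children who wear ankle devices. The size of that group is unknown, and it shrinks to the extent that active AD at the ankle leads to the device being left off.

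The conclusion rests on the form printed in the appendix being the one used, with no separate ankle version; the documents show none. Compliance, safety, the primary analysis and the sample size are unaffected. This is an optional improvement.

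**What to change.** For children aged 3 months to under 2 years who wore an ankle device, add two items to the ODCQ at V05: an ankle version of item 1 (0 to 5 comfort) and an ankle version of item 3 (four-level willingness). Leave the wrist items unchanged, so that they stay comparable across ages and with the caregiver form. Optionally split item 2 into one answer for wrist and one for ankle. Summarise the responses by location, and report the number of children whose caregivers answered the ankle items. If only one item can be added, the comfort rating is the more useful.

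The cost is two extra caregiver questions (three if item 2 is split), asked once at an existing visit. Because the form is part of the protocol appendix, the change needs an amendment approved under Section 11.2, and it is sensible to bundle it with any other amendment. Children who finish before the change takes effect would lack the new items, so the summary should state its denominator.

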Appendix C. QUALITY OF LIFE (QoL) QUESTIONNAIRES

[figure not shown]
Dermatology-related QoL scores will be collected during the study.

- The Dermatitis Family Impact Questionnaire will be completed by all parents/guardians of participants aged 3 months - \leq 11 years, based on the age at enrollment.
- The CDLQI will be completed by all participants aged \geq 4 - \leq 11 years
- The IDLQI will be completed by all participants aged 3 months - $<$ 4 years

The following Quality-of-Life (QoL) questionnaires will be administered to the participant and/or parent/guardian of the participant on a supplied tablet (the paper form is shown below for review). Directions on how to complete the assessments will be provided to the participant and/or parent/guardian. The Schedule of Activities identifies the administration timing for the various assessments.

CHILDREN'S DERMATOLOGY LIFE QUALITY INDEX

The aim of this questionnaire is to measure how much your skin problem has affected you OVER THE LAST WEEK. Please tick one box for each question.

1. Over the last week, how itchy , " scratchy ", sore or painful has your skin been?	Very much  Quite a lot  Only a little  Not at all 
2. Over the last week, how embarrassed or self conscious , upset or sad have you been because of your skin?	Very much  Quite a lot  Only a little  Not at all 
3. Over the last week, how much has your skin affected your friendships ?	Very much  Quite a lot  Only a little  Not at all 
4. Over the last week, how much have you changed or worn different or special clothes/shoes because of your skin?	Very much  Quite a lot  Only a little  Not at all 
5. Over the last week, how much has your skin trouble affected going out , playing , or doing hobbies ?	Very much  Quite a lot  Only a little  Not at all 
6. Over the last week, how much have you avoided swimming or other sports because of your skin trouble?	Very much  Quite a lot  Only a little  Not at all 
7. Last week,  was it school time?  If school time: Over the last week, how much did your skin problem affect your school work ? OR was it holiday time?  If holiday time: How much over the last week, has your skin problem interfered with your enjoyment of the holiday ?	Prevented school  Very much  Quite a lot  Only a little  Not at all 
8. Over the last week, how much trouble have you had because of your skin with other people calling you names , teasing , bullying , asking questions or avoiding you ?	Very much  Quite a lot  Only a little  Not at all 
9. Over the last week, how much has your sleep been affected by your skin problem?	Very much  Quite a lot  Only a little  Not at all 
10. Over the last week, how much of a problem has the treatment for your skin been?	Very much  Quite a lot  Only a little  Not at all 

Please check that you have answered EVERY question. Thank you.

Subject ID: _____ Date: _____ Technician Initials: _____

"Dermatitis Family Impact Questionnaire"

Child's Name: **LEAVE BLANK** Mother/Father/Carer Date: Score

The aim of this questionnaire is to measure how much your child's skin problem has affected you and your family OVER THE LAST WEEK. Please tick one box for each question.

1. Over the last week , how much effect has your child having eczema had on housework , e.g. washing, cleaning.	Very much 
	A lot 
	A little 
	Not at all 
2. Over the last week , how much effect has your child having eczema had on food preparation and feeding .	Very much 
	A lot 
	A little 
	Not at all 
3. Over the last week , how much effect has your child having eczema had on the sleep of others in family .	Very much 
	A lot 
	A little 
	Not at all 
4. Over the last week , how much effect has your child having eczema had on family leisure activities , eg swimming.	Very much 
	A lot 
	A little 
	Not at all 
5. Over the last week , how much effect has your child having eczema had on time spent on shopping for the family .	Very much 
	A lot 
	A little 
	Not at all 
6. Over the last week , how much effect has your child having eczema had on your expenditure , eg costs related to treatment, clothes, etc.	Very much 
	A lot 
	A little 
	Not at all 
7. Over the last week , how much effect has your child having eczema had on causing tiredness or exhaustion in your child's parents/carers.	Very much 
	A lot 
	A little 
	Not at all 
8. Over the last week , how much effect has your child having eczema had on causing emotional distress such as depression, frustration or guilt in your child's parents/carers.	Very much 
	A lot 
	A little 
	Not at all 
9. Over the last week , how much effect has your child having eczema had on relationships between the main carer and partner or between the main carer and other children in the family.	Very much 
	A lot 
	A little 
	Not at all 
10. Over the last week , how much effect has helping with your child's treatment had on the main carer's life.	Very much 
	A lot 
	A little 
	Not at all 

Please check you have answered **EVERY** question. Thank you
© M.S. Lewis-Jones, A.Y. Finlay 1995

Subject ID: _____

Date: _____

Technician Initials: _____

INFANTS' DERMATITIS QUALITY OF LIFE INDEX (IDQOL)Name: **LEAVE BLANK**

Date:

IDQOL
SCORE

The aim of this chart is to record how your child's dermatitis has been. Each question concerns THE LAST WEEK ONLY. Please could you answer every question.

Dermatitis Severity

Over the last week, **how severe** do you think your child's dermatitis has been?, i.e. how red, scaly, inflamed or widespread.

Extremely severe
Severe
Average
Fairly good
None

Life Quality Index

1. Over the last week, how much has your child been **itching and scratching**?

All the time
A lot
A little
None

2. Over the last week, what has your child's **mood** been?

Always crying, extremely difficult
Very fretful
Slightly fretful
Happy

3. Over the last week approximately how much **time** on average has it taken **to get your child off to sleep** each night?

More than 2 hrs
1 - 2 hrs
15mins - 1 hr
0-15mins

4. Over the last week, what was the **total time** that your child's **sleep was disturbed** on average each night?

5 hrs or more
3 - 4 hrs
1 - 2 hrs
Less than 1 hour

5. Over the last week, has your child's eczema interfered with **playing or swimming**?

Very much
A lot
A little
Not at all

6. Over the last week, has your child's eczema interfered with your child **taking part in or enjoying other family activities**?

Very much
A lot
A little
Not at all

7. Over the last week, have there been problems with your child at **mealtimes** because of the eczema?

Very much
A lot
A little
None

8. Over the last week, have there been problems with your child caused by the **treatment**?

Very much
A lot
A little
None

9. Over the last week, has your child's eczema meant that **dressing and undressing** the child has been **uncomfortable**?

Very much
A lot
A little
None

10. Over the last week how much has your child having eczema been a problem at **bathtime**?

Very much
A lot
A little
None

Please can you check that you have answered every question.

© M.S. Lewis-Jones, A.Y. Finlay Jan 2000

Subject ID: _____

Date: _____

Technician Initials: _____

OBSERVER REPORTED GLOBAL IMPRESSION OF CHANGE (OGIC)

Place an X in the box you feel most closely describes any change which the child has experienced. Take into account all change, whether or not you believe it is entirely due to drug treatment.

Select only ONE response.

Since the start of the study, the child's atopic dermatitis is:

Very much improved	
Much improved	
Minimally improved	
No change	
Minimally worse	
Much worse	
Very much worse	

Mobile Device Proficiency Questionnaire (MDPQ-16)

About the MDPQ

This questionnaire asks about your ability to perform a number of tasks with a mobile device.

What is a Mobile Device?

A mobile device is a device that allows you to perform many of the same tasks as a standard computer but without the use of a physical keyboard and mouse. Instead, these devices use a touchscreen as their interface between the user and computer programs (called Apps – short for applications).

Mobile devices come in many sizes. Depicted above are two different sized tablets, as well as a smartphone. These are the types of devices we are interested in.

ROQUE, N. & BOOT, W.R. (IN PRESS). A NEW TOOL FOR ASSESSING MOBILE DEVICE PROFICIENCY IN OLDER ADULTS: THE MOBILE DEVICE PROFICIENCY QUESTIONNAIRE (MDPQ). JOURNAL OF APPLIED GERONTOLOGY.

Subject ID: _____ Date: _____
Technician Initials: _____

Please answer each question by placing an X in the box that is most appropriate.

If you have not tried to perform a task with a mobile device or do not know what a task is, please mark "NEVER TRIED", regardless of whether or not you think you may be able to perform the task. Remember, you are rating your ability to perform each of these tasks specifically using a mobile device (tablet or smartphone).

1. Mobile Device Basics

Using a mobile device I can:	Never tried (1)	Not at all (2)	Not very easily (3)	Somewhat easily (4)	Very easily (5)
a. Navigate onscreen menus using the touchscreen					
b. Use the onscreen keyboard to type					

2. Communication

Using a mobile device I can:	Never tried (1)	Not at all (2)	Not very easily (3)	Somewhat easily (4)	Very easily (5)
a. Send emails					
b. Send pictures by email					

Subject ID: _____ Date: _____
Technician Initials: _____

3. Data and File Storage

Using a mobile device I can:	Never tried (1)	Not at all (2)	Not very easily (3)	Somewhat easily (4)	Very easily (5)
a. Transfer information (files such as music, pictures, documents) on my mobile device to my computer					
b. Transfer information (files such as music, pictures, documents) on my computer to my mobile device					

4. Internet

Using a mobile device I can:	Never tried (1)	Not at all (2)	Not very easily (3)	Somewhat easily (4)	Very easily (5)
a. Find information about my hobbies and interests on the Internet					
b. Find health information on the Internet					

Subject ID: _____ Date: _____
 Technician Initials: _____

5. Calendar

Using a mobile device I can:	Never tried (1)	Not at all (2)	Not very easily (3)	Somewhat easily (4)	Very easily (5)
a. Enter events and appointments into a calendar					
b. Check the date and time of upcoming and prior appointments					

6. Entertainment

Using a mobile device I can:	Never tried (1)	Not at all (2)	Not very easily (3)	Somewhat easily (4)	Very easily (5)
a. Use the device's online "store" to find games and other forms of entertainment (e.g. using Apple App Store or Google Play Store)					
b. Listen to music					

Subject ID: _____ Date: _____
Technician Initials: _____

7. Privacy

Using a mobile device I can:	Never tried (1)	Not at all (2)	Not very easily (3)	Somewhat easily (4)	Very easily (5)
a. Setup a password to lock/unlock the device					
b. Erase all Internet browsing history and temporary files					

8. Troubleshooting & Software Management

Using a mobile device I can:	Never tried (1)	Not at all (2)	Not very easily (3)	Somewhat easily (4)	Very easily (5)
a. Update games and other applications					
b. Delete games and other applications					

Subject ID: _____ Date: _____ Technician Initials: _____

Table 1. FLACC Scale

Categories	Scoring		
	0	1	2
Face	No particular expression or smile	Occasional grimace or frown, withdrawn, disinterested	Frequent to constant quivering chin, clenched jaw
Legs	Normal position or relaxed	Uneasy, restless, tense	Kicking, or legs drawn up
Activity	Lying quietly, normal position, moves easily	Squirming, shifting back and forth, tense	Arched, rigid or jerking
Cry	No cry (awake or asleep)	Moans or whimpers; occasional complaint	Crying steadily, screams or sobs, frequent complaints
Consolability	Content, relaxed	Reassured by occasional touching, hugging or being talked to, distractable	Difficult to console or comfort

Each of the five categories (F) Face; (L) Legs; (A) Activity; (C) Cry; (C) Consolability is scored from 0-2, which results in a total score between zero and ten.

Subject ID: _____

Date: _____

PP-NRS for Caregivers ages 18-75:

Select the number that “On a scale of 0 to 10, with 0 being “no itch” and 10 being “worst itch imaginable”, how would you rate your itch at the worst moment during the previous 24 hours?

										
0	1	2	3	4	5	6	7	8	9	10
No Itch										Worst Itch Imaginable

Subject ID: _____

Date: _____

Technician Initials: _____

The University of
Nottingham

UNITED KINGDOM · CHINA · MALAYSIA

POEM for proxy completion (e.g by parent)

Patient Details: _____

Leave blank

Date: _____

Please circle one response for each of the seven questions below about your child's eczema. If your child is old enough to understand the questions then please fill in the questionnaire together. Please leave blank any questions you feel unable to answer.

1. Over the last week, on how many days has your child's skin been itchy because of their eczema?

No days 1-2 days 3-4 days 5-6 days Every day

2. Over the last week, on how many nights has your child's sleep been disturbed because of their eczema?

No days 1-2 days 3-4 days 5-6 days Every day

3. Over the last week, on how many days has your child's skin been bleeding because of their eczema?

No days 1-2 days 3-4 days 5-6 days Every day

4. Over the last week, on how many days has your child's skin been weeping or oozing clear fluid because of their eczema?

No days 1-2 days 3-4 days 5-6 days Every day

5. Over the last week, on how many days has your child's skin been cracked because of their eczema?

No days 1-2 days 3-4 days 5-6 days Every day

6. Over the last week, on how many days has your child's skin been flaking off because of their eczema?

No days 1-2 days 3-4 days 5-6 days Every day

7. Over the last week, on how many days has your child's skin felt dry or rough because of their eczema?

No days 1-2 days 3-4 days 5-6 days Every day

Total POEM Score (Maximum 28): _____

Patient-Oriented Eczema Measure

UNITED KINGDOM • CHINA • MALAYSIA

POEM for proxy completion (e.g by parent)

How is the scoring done?

Each of the seven questions carries equal weight and is scored from 0 to 4 as follows:

No days	= 0
1-2 days	= 1
3-4 days	= 2
5-6 days	= 3
Every day	= 4

Note:

- If one question is left unanswered this is scored 0 and the scores are summed and expressed as usual out of a maximum of 28
- If two or more questions are left unanswered the questionnaire is not scored
- If two or more response options are selected, the response option with the highest score should be recorded

What does a poem score mean?

To help patients and clinicians to understand their POEM scores, the following bandings have been established (see references below):

• 0 to 2	= Clear or almost clear
• 3 to 7	= Mild eczema
• 8 to 16	= Moderate eczema
• 17 to 24	= Severe eczema
• 25 to 28	= Very severe eczema

Do I need permission to use the scale?

Whilst the POEM scale is protected by copyright, it is freely available for use and can be downloaded from: www.nottingham.ac.uk/dermatology

We do however ask that you register your use of the POEM by e-mailing [contact] with details of how you would like to use the scale, and which countries the scale will be used in.

References

© The University of Nottingham. The Patient Oriented Eczema Measure (POEM) scale is free to use. Permission is granted to reproduce and/or redistribute this material in its entirety without modification. Any use which falls outside this remit requires the express consent of the copyright owner.

[figure not shown]
[figure not shown]
Dosing record sheet

Subject ID: _____

Instructions: Everyday, you will be applying the ointment twice a day on all affected areas in thin even layers except on the eyes, mouth, and vagina. Do not apply the study ointment to the face within 1 or 2 fingers away from the mouth, or hands/fingers to avoid inadvertent ingestion of the ointment. Wash your hands after everytime you apply the ointment; if you are breastfeeding, use the provided gloves to apply the ointment. Following diaper change, any study ointment inadvertently wiped off soiled skin should not be reapplied until the next scheduled dose. In the case of rash in the diaper area without AD involvement, standard treatments may be applied, and agree to refrain from applying diaper rash creams, lotions, ointments, powders, etc. where AD lesions are present, unless the lesions are on locations where the study ointment may not be applied (face within 1 or 2 fingers away from the mouth and hands/fingers).

[figure not shown]
Every time you apply the ointment, please record the date and time on a separate sheet. On each dosing record sheet, please circle on the pictures where you applied the ointment each application time.

Date: _____ Time: _____

[figure not shown]

